## Abbreviations and Definitions of Terms

Abbreviation	Definition
HF	Heart failure
HRQOL	health related quality of life
RCT	Randomized controlled trial
G6PD	glucose-6-phosphate dehydrogenase deficiency
UNCH	University of North Carolina at Chapel Hill Hospital
MLHFQ	Minnesota Living with Heart Failure questionnaire
MSAS-HF	Memorial Symptom Assessment Scale—Heart Failure
ELISA	Enzyme-linked immunosorbent assay
HIPAA	Health Insurance Portability and Accountability Act
EDTA	Ethylenediaminetetraacetic acid
BHT	Butylated hydroxytoluene

## **1. BACKGROUND:**

### **Heart failure**

Although significant advancements in morbidity and mortality statistics have been established with medical treatment, HF remains a prevalent, morbid, and costly condition. Currently, 6.5 million Americans have heart failure (HF), 50% are readmitted within 6 months of hospital discharge for exacerbations of HF. Thus, hospitals are financially penalized for HF readmissions within 30 days based on the Readmissions Reduction Program initiated by the Centers for Medicare & Medicaid Services. Moreover, patients with HF continue to be symptomatic even after optimization of medical treatment. These symptoms are associated with frequent hospitalization, as well as decreased health related quality of life (HRQOL). Therefore, HF symptom reduction is still the major target of treatment to reduce frequent re-hospitalizations and improve HRQOL.

### **Vitamin C Supplementation**

Mean serum vitamin C level was significantly lower in patients with HF compared to those with other non-HF chronic illness. Up to 39% of patients with HF had vitamin C deficiency. Many studies have shown that higher vitamin C levels are associated with improved endothelial function. There was a significant positive correlation between cardiac function and serum vitamin C level. Furthermore, in a prospective study in HF, vitamin C deficiency predicted shorter cardiac event-free survival.

In two intervention studies in patients with HF, investigators found that vitamin C supplementation increased serum vitamin C level and also improved endothelial function. Other interventional studies also provided evidence that vitamin C supplementation not only improved cardiac function, but also reduced oxidative stress in patients with HF. However, most of these trials tested effects of high dose vitamin C supplementation via intravenous or intra-arterial administration. Only two trials with very small sample size (n=10) tested oral, 1 month vitamin C supplementation and found vitamin C supplementation increased serum vitamin C level and also improved endothelial function, although neither study controlled for confounders such as age, race, sex, BMI or social status.

### **Preliminary Study**

The PI has conducted a preliminary study that serves as the foundation for this feasibility pilot proposal. This was an observational study in which we collected dietary vitamin C intake from a 4-day food diary, symptom burden using the Memorial Symptom Assessment Scale—Heart Failure, and HRQOL using the Minnesota Living with Heart Failure questionnaire at baseline, and prospectively followed cardiac hospitalization and death for up to 4 years in 264 patients with HF. In this study, 41% of HF patients had vitamin C deficiency. Patients with vitamin C deficiency had higher symptom burden (p = .05), worse HRQOL (p < .001) and were about twice as likely to have a cardiac event compared to patients with adequate vitamin C intake (p = .015). This study demonstrated the high prevalence and worse consequences of vitamin C deficiency in patients with HF.

## **2. STUDY OBJECTIVE**

The purpose of this study is to test a low-cost, simple vitamin C supplementation intervention, that is, comparing placebo to 500mg/day vitamin C and 1gram/day vitamin C daily to assess feasibility and acceptability of vitamin C supplementation and effects on serum vitamin C level, cardiac function, HF symptoms, and HRQOL. Our specific aim 1 is to test the effect of a vitamin C supplementation intervention on the primary outcome (serum vitamin C level) from baseline to 3-month follow-up among 3 groups (0.5 g, 1 g vitamin C, and placebo).

Specific aim 2 is to test the effect of a vitamin C supplementation intervention on the secondary outcomes (HF symptom burden, health related quality of life (HRQOL), cardiac function, and oxidative stress) from baseline to 3-month follow-up among 3 groups. Specific aim 3 is to collect data to assess feasibility (recruitment, retention, attrition rates).

### 3. INVESTIGATIONAL PLAN

**Design.** This project is a feasibility pilot study to test the effects of vitamin C supplementation, and to obtain initial estimates of effect size to support a future RCT. The proposed vitamin C supplementation intervention study is a three-group, single blind, placebo controlled prospective design (control n=14, Vit C 500mg n=14, Vit C 1000mg n=14). The most commonly tested dose of vitamin C in current trials on vitamin C supplementation is 1 g/day. The primary endpoint to evaluate the effect of vitamin C supplementation is serum vitamin C level. The secondary outcomes include HF symptom burden, HRQOL, cardiac function, and oxidative stress. The variables would be measured in person at baseline and at 3 months include: HF symptom burden, HRQOL, PROMIS fatigue, depression and sleep disturbance, serum vitamin C level, biomarker of cardiac function (i.e., cardiac output using impedance cardiograph) and oxidative stress (8-iso-PGF2a isoprostane, see below in detail), as well as demographic, clinical, and other variables that can affect study outcomes (e.g., age, gender, race/ethnicity, body mass index, serum creatinine) and medications. HF symptom burden and HRQOL will also be measured at Month 1 and 2 by phone. We will also collect data to assess feasibility (recruitment, retention, attrition rates).

**Sample and Setting.** A total of 42 participants (14 per group) will be randomly assigned to either the control or the intervention group. Patients with HF will be recruited at the University of North Carolina Hospital internal medicine/cardiology outpatient clinics.

**Inclusion/Exclusion Criteria.** Inclusion criteria include patients (a) have a diagnosis of chronic HF. The diagnosis and etiology of chronic HF will be confirmed by a HF cardiologist using established criteria, (b) have undergone evaluation of HF and optimization of medical therapy, (c) are not taking any vitamin C supplementation at all or are willing to stop taking their current vitamin C supplementation, (d) able to read and speak English, (e) have >1 month from any inpatient hospitalization, (e) treating cardiology healthcare provider indicates the individual is a good candidate for this study that involves 3 months of vitamin C supplement of 500 mg/day, 1g/day, or placebo, (f) Per treating healthcare provider's assessment, patient's projected lifespan is greater than or equal to 6 months.

Exclusion criteria include: (a) stage D HF or New York Heart Association (NYHA) functional class IV, (b) history of renal stones or renal disease (serum creatinine >1.5), (c) history of glucose-6-phosphate dehydrogenase deficiency (G6PD) and (d) cognitive impairment that precludes giving informed consent or ability to follow protocol instructions, (e) originally taking vitamin C 500mg/day or more, (f) women who are pregnant.

Female patients with HF are considered past child-bearing potential: 1) if they are ≥60yrs of age or 2) if they are age 50 to 59 years and have not menstruated for 12 months (will confirm by self-report). For women < 50 years old (with child-bearing potential), we will confirm by self-report that they are not pregnant and confirm this by completing a urine pregnancy test prior to enrollment and assess for likelihood of pregnancy on a monthly basis.

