### 4. INTERVENTION

The intervention is designed to complement medical management. Therefore, all patients will continue to be medically managed by their health care provider as usual.

Participants will have a visit at baseline and Month 3 (with some flexibility to do the final visit at 3 months +/- 1 month) coordinated with their regular clinic visits that are typically scheduled every 3 months.

**Vitamin C supplementation.** Throughout the study, patients will continue with their routine diets. Patients randomized to the intervention groups will be provided with 4-month supply of either Vitamin C 500mg or Vitamin C tablets (1000mg) in a bottle and the control group will be provided placebo tablets in a bottle. All participants in the intervention group will be instructed to take one vitamin C tablet (500mg/ day or 1000mg/day) with one meal daily from baseline for 3 months and all control group participants will be instructed to take one placebo tablet with one meal daily from baseline to 3 months. Participants will return their un-used investigational drugs on the day of their 3-month follow-up. We will count remaining pills to determine participant's treatment adherence with both the vitamin C supplementation (500mg or 1000mg) and control (placebo) groups. After counting the pills, the un-used pills will be delivered to the Investigational Drug Services (IDS) pharmacy to dispose. We will draw blood to measure serum vitamin C level to determine drug accountability.

**Role of the Investigational Drug Services (IDS).** The IDS will provide oversight for the storage, dispensing, labeling, distribution and disposal of all investigational medications (vitamin C tablets and placebo) for the study.

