## **5. PROCEDURES AND RECRUITMENT STRATEGY**

Permission for this study will be obtained from the University of North Carolina at Chapel Hill Institutional Review Board. A dedicated and trained research assistant will recruit HF patients from the UNCH clinics. A list of HF patients who will come to the UNCH clinics will be generated and obtained from the staff in charge for the scheduling information in the clinics one week before patients' visits. On the day that the potential participants come to the clinic, the research assistant will screen the potential participant's eligibility based on inclusion and exclusion criteria. The research assistant also will consult with the potential participant's treating healthcare provider to make sure the potential participant is appropriate for the study and patient's projected lifespan is greater than or equal to 6 months. Once the research assistant confirms the potential participants are eligible and gets approval from the provider, the research assistant will approach and briefly explain the study to recruit potential participants while they wait to see their physicians. If potential participants are interested in participation, the research assistant will then confirm eligibility. For eligible patients, study requirements will be explained in detail. If the patient agrees to participate, a signed informed consent will be obtained based on consent process (see below) and we will administer the survey, measure cardiac impedance and obtain the blood samples. All eligible patients will be randomized to either the control group or to the intervention group using the Medsharing application for clinical trials.

**Baseline visit.** Data on socio-demographics, clinical characteristics medications, symptom burden, PROMIS depression, fatigue, and sleep disturbance, HRQOL, will be collected at the beginning of the visit and blood will be drawn to measure serum vitamin C level and oxidative stress (8-iso-PGF2a isoprostane). All participants will be asked to return their respective supplementation bottles to the research assistant at Month 3. We will count pills to determine patient adherence to taking the placebo or vitamin C supplementation.

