**Follow up phone call (Month 1 and 2).** Follow up phone calls will occur within 1 week after enrollment to follow-up whether they are taking the investigational pills (vitamin C or placebo) daily and whether they have any adverse events from taking the investigational pills, as well as at Month 1 and 2. The research assistant will inquire about general welfare and collect data on HF symptom burden and HRQOL (for both groups).

***Month 3 visit.*** Data on socio-demographics, clinical characteristics medications, symptom burden, PROMIS depression, fatigue, and sleep disturbance, HRQOL, will be collected at the beginning of the visit and blood will be drawn to measure serum vitamin C level and oxidative stress (8-iso-PGF2a isoprostane). All participants will be asked to return their vitamin C (or placebo) bottle to the research assistant at Month 3. We will count pills to determine their adherence to taking the placebo or vitamin C supplementation.

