The adverse event information will be reviewed in our monthly team meeting to monitor subject safety. The PI will also monitor the rate of AEs occurring in this study and decide if it is reasonable in light of the rate of AEs in the current literature to continue the study with the medical monitor's input.

The research assistant is responsible to report any AE related to the study to [name] and the PI. The PI will work with the medical monitor to evaluate the event and make a determination of relatedness if the event is related to the study, as it occurs and for notifying the Associate Dean for Research of the UNC School of Nursing and UNC IRB of the occurrence of any adverse event. A scale on relatedness ranging from "Not related to" to "Definitely related to" (Not related to, probably not related to, possibly related to, definitely related to) will be used to evaluate relatedness. Any "definitely related" and "possibly related" events will be reported to the UNC IRB.

The PI will report to the UNC IRB any adverse events that are (1) unexpected, (2) related or possibly related to participation in the research, and (3) serious or suggest that there are new or increased risk(s) to subjects.

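### The plan is single blind without saying who is blinded, and nothing masks the staff who collect patient-reported outcomes and adverse events, although the pharmacy is placed to hold the code

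*Combined protocol and SAP*

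**What the plan says.** Section 3 sets out a "three-group, single blind, placebo controlled prospective design" with three equal arms ("control n=14, Vit C 500mg n=14, Vit C 1000mg n=14"). The blinded party is not named. The combined protocol and SAP does not describe matching tablets, coded bottles, restricted access to the assignment or a way to break the code.

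The parts of the plan that bear on masking are:

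- **Assignment (section 5).** Patients are "randomized to either the control group or to the intervention group using the Medsharing application for clinical trials". Who sees the result is not stated.
- **Instructions (section 4).** These are worded by arm: "All participants in the intervention group will be instructed to take one vitamin C tablet (500mg/ day or 1000mg/day"; the control group has its own sentence about placebo.
- **Pharmacy (section 4).** "The IDS will provide oversight for the storage, dispensing, labeling, distribution and disposal of all investigational medications". Every arm takes one tablet a day, and unused pills go to IDS after they have been counted.
- **Data collection (section 5).** At the Month 1 and 2 calls, "The research assistant will inquire about general welfare and collect data on HF symptom burden and HRQOL (for both groups". The calls also cover pill-taking and adverse events. Bottles are returned to the research assistant at Month 3.
- **Adverse events (section 8).** The medical monitor grades severity. On causality, "The PI will work with the medical monitor to evaluate the event and make a determination of relatedness".
- **Analysis (section 9).** Symptom burden and HRQOL are two of the four secondary endpoints. Adverse event frequencies are compared among the three groups. Interim findings go to the medical monitor.

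**The concern.** In a placebo-controlled trial called single blind, the usual reading is that the patient is the blinded party. Nothing in this plan then stops the staff from knowing the arm. The person in the research assistant role would know, or could find out, what the patient is taking while asking about symptoms, quality of life and side effects. Answers given in an interview can be affected by how a question is put, followed up and recorded.

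Two things are at stake. The first is Aim 2, where symptom burden and HRQOL are compared across arms. The second is the adverse event comparison. Section 8 defines an adverse event partly by whether it could be related to the intervention, so a view about the arm can affect whether an open-ended complaint is pursued and counted.

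Section 3 says the pilot is meant to give initial effect sizes for a later RCT. An assessment bias would pass into those estimates, and a larger later trial planned on them would inherit it.

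**Working it through.** **1. The plan's own figure.** Section 9 states 80% power for the ANOVA F test with 42 patients, alpha 0.05 and effect size 0.5. Reading the effect size as Cohen's f, the noncentrality is f² × N = 0.25 × 42 = 10.5 on 2 and 39 degrees of freedom. This gives 80.3% power, so the figure reproduces. It does not depend on blinding, and masking staff would change neither sample size nor power.

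**2. Which outcomes are exposed.**

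| Outcome | How obtained | Exposure if staff know the arm |
|---|---|---|
| Serum vitamin C (primary), isoprostane | ELISA, section 7 | Low |
| Cardiac output | Impedance device, section 7 | Low |
| Symptom burden, HRQOL at Months 1 and 2 | Phone, by the research assistant, section 5 | Direct, to the extent that these scores enter the analysis |
| Symptom burden, HRQOL at Month 3 | Self-report at the visit, or by phone or mail if visits are barred, sections 5 and 6 | Possible; who administers it is not stated |
| Adverse event frequency | Yes/no checklist plus an open item, section 10 | Possible, through what is asked, followed up and counted |

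Aim 2 is worded as baseline to 3 months. Section 9 does not say whether the Month 1 and 2 scores enter the repeated-measures ANOVA.

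**3. Illustration of size.** The documents contain no estimate of assessment bias, so the shift is an assumption. Suppose there is no true effect, SD 1, and both active arms are shifted by d relative to placebo. The group means are (0, d, d), with overall mean 2d/3. The noncentrality of the one-way F test is

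14 × [(2d/3)² + (d/3)² + (d/3)²] = 14 × (2/3) × d² = 9.33 d².

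The critical value of F(2, 39) at 5% is 3.238.

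| Assumed shift d (SD) | Noncentrality | Rejection rate at nominal 5% |
|---|---|---|
| 0.1 | 0.093 | 5.7% |
| 0.2 | 0.373 | 7.7% |
| 0.3 | 0.840 | 11.3% |
| 0.4 | 1.493 | 16.8% |

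**4. Effect on the estimates.** The standard error of a difference between two arms, in SD units, is √(1/14 + 1/14) = 0.378. A shift of 0.2 to 0.4 SD is therefore 0.2/0.378 = 0.53 to 0.4/0.378 = 1.06 standard errors. Its full amount is added to the estimated active-versus-placebo difference.

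**The case against.** The strongest reply is that this is a 42-patient feasibility pilot with a laboratory primary endpoint and a placebo arm, and that the documents show an unspecified masking plan, not unmasked staff. Several parts of that reply stand, and they rule out stronger readings that a reader might infer:

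- **That staff know the arm.** The documents do not say so. They only fail to exclude it.
- **That the pharmacy labels and dispenses every bottle.** Section 4 gives IDS oversight of those steps, which is less than that.
- **That the research assistant counts the pills.** The assistant receives the bottles; the text does not say who counts.
- **That severity and relatedness grading biases the arm comparison directly.** Section 9 compares frequencies, not grades. The supported route is narrower: which events are elicited and counted under the section 8 definition.
- **That all of Aim 2 rests on interviews.** The phone scores are from Months 1 and 2, while the stated contrast is baseline to Month 3. Interviewing at Month 3 is not established.
- **That the true error rate is 7.7% to 16.8%.** Those figures follow from an assumed shift and a simplified test.

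It is also fair to say that tablet appearance is not described, so full masking cannot be promised, and that masking the medical monitor has to be reconciled with the interim review. None of this gives a reason to leave the staff unmasked.

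**Conclusion.** The point holds in limited form and is worth acting on. If followed as written, the plan leaves the patient-reported secondary outcomes and adverse event ascertainment open to bias from staff who may know the arm. The primary endpoint, oxidative stress and cardiac output are much less exposed, and the stated power is unaffected.

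The size of any bias cannot be derived from the documents. The 7.7%, 11.3% and 16.8% figures assume an equal shift of 0.2, 0.3 or 0.4 SD in both active arms and use a one-way F test on a single score in place of the planned repeated-measures ANOVA. They show only that a modest shift would matter with 14 per arm. How far the phone scores contribute depends on whether they enter that analysis.

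This goes beyond a request for missing detail. A better arrangement is available at small cost, because IDS already oversees the relevant steps and all arms take one tablet a day.

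**What to change.** This is a cheap improvement.

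1. State in section 3 who is masked: participants, the research assistant, the investigator and the assay staff.
2. Send the randomisation result only to IDS.
3. Use arm-neutral coded bottle labels, and give every participant the existing once-daily, with-a-meal instruction in identical words that do not name the product.
4. Have IDS do the pill count, since unused pills already go there.
5. Withhold individual serum vitamin C results from outcome collectors until data lock. Section 4 uses those results for drug accountability, so they could reveal the arm.
6. Have adverse events graded masked to arm. Because the medical monitor also receives the interim findings, supply these by coded group, and describe a route through IDS for unmasking when safety requires it.
7. State whether the Month 1 and 2 scores enter the Aim 2 analysis.

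The cost is protocol wording, a code-break route and a little extra pharmacy work. No additional patients are needed. If the tablets differ in appearance, masking will be incomplete, because patients may describe them. In that case, or if any staff role cannot be masked, give the reason and report it as a limitation of the symptom, HRQOL and adverse event results.

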## **8. SAFETY EVALUATIONS**

All participants will receive a phone call within 1 week after enrollment, and also at Month 1 and Month 2 to follow-up whether they are taking the investigational pills (vitamin C or placebo) daily and whether they have any adverse events from taking the investigational pills (see checklist in Appendix). If any adverse events were found/reported, we will follow them per recommendations of the medical monitor until the event resolves. [name], a nurse practitioner with specialty in heart failure management at UNC Meadowmont Cardiology clinic will serve as a medical monitor on this study. Any adverse event will be reported to [name] in 72 hours or less. [name] will determine the severity of the adverse events and advise whether the participant needs to stop taking the investigational pills, withdraw from the study, or any medical treatment is needed. We will follow [name]' advice immediately.

When subjects have AE (define as new signs and symptoms after taking investigational drugs, such as digestive distress--diarrhea, nausea, abdominal bloating and any other unanticipated adverse events that could possibly be related to the intervention). We will report to

[name] to determine the severity of the AEs (see below). When mild AE is determined, subjects will continue to take their investigational drugs without further treatment and the RA will keep following up subject's AE until AE resolves. When moderate AE is determined, we will ask subjects to stop taking their investigational drug, advise them to seek medical treatment, and continue to follow up until the AE resolves. If severity of any AE is more than moderate, we will ask subjects to seek for emergent medical treatment.

- Mild Adverse Event – Event results in mild or transient discomfort, not requiring intervention or treatment; does not limit or interfere with daily activities (e.g., insomnia, mild headache).
- Moderate Adverse Event – Event is sufficiently discomforting so as to limit or interfere with daily activities; may require interventional treatment (e.g., fever requiring antipyretic medication).
- Severe and undesirable Adverse Event – Event results in significant symptoms that prevents normal daily activities; may require hospitalization or invasive intervention (e.g., anemia resulting in blood transfusion).

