**Patient Safety and Confidentiality.** All private health information (PHI) will be kept strictly confidential and subject to the Health Insurance Portability and Accountability Act (HIPAA). All study data in transit will be stored on an encrypted lap top computer stored and locked within the office of the study PI. All transit study data will be back up to the secure SON server that is password protected and maintained by information technology support and then be deleted from the encrypted laptop computer within 72 hours after data are collected. The secure SON server can only be accessed by study personnel on this study. Any new signs or symptoms reported by the patient to the research team will be promptly communicated to the patient's health care team. At the baseline visit, patients will be assessed for any vitamin supplementation, serum creatinine and history of kidney stones. If subjects are currently taking a vit C supplement, we will advise them to stop taking any vitamin C supplement while they are on the study. We also will carefully review with the subjects if they are taking any multivitamin that contains vitamin C and advise them to stop taking any multivitamin that contains vitamin C. Although vitamin C is a water-soluble vitamin, we have implemented these steps to insure safety before randomization.

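### Pregnancy testing stops at age 50, but the protocol's own definition leaves women of 50 to 59 with recent menses not past child-bearing potential

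*Combined protocol and SAP*

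**What the plan says.** All the relevant rules are in Section 3, under Inclusion/Exclusion Criteria.

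- **Exclusion (f)** removes "women who are pregnant", with no age limit.
- **The definition** has two routes. The first is age: "Female patients with HF are considered past child-bearing potential: 1) if they are ≥60yrs of age". The second is age with menstrual history: "if they are age 50 to 59 years and have not menstruated for 12 months", established by self-report.
- **The checks** come in the next sentence: "For women < 50 years old (with child-bearing potential), we will confirm by self-report that they are not pregnant". The same sentence adds "completing a urine pregnancy test prior to enrollment and assess for likelihood of pregnancy on a monthly basis".

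Section 5 has the research assistant screen each patient's "eligibility based on inclusion and exclusion criteria" and obtain the treating provider's agreement before approaching the patient. Section 8 says that at baseline "patients will be assessed for any vitamin supplementation, serum creatinine and history of kidney stones". Its phone calls, within 1 week and at Months 1 and 2, ask about pill-taking and "whether they have any adverse events from taking the investigational pills".

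**The concern.** The definition and the checks should divide women at the same line: those past child-bearing potential need no check, and everyone else gets one. Here the definition runs to 60 with a menstrual condition from 50, while the checks stop at 50. Women of 50 to 59 who have menstruated within 12 months fall between the two.

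The stake is participant safety. If staff follow the text, an unrecognised pregnancy in such a woman could be missed at entry or during the 3 months of study tablets. A woman of 49 with the same menstrual history would be tested and then reviewed monthly. No estimate or test in the analysis depends on this.

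**Working it through.** No formula applies and the plan gives no figure to reproduce. The check has three steps.

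**1. Compare the definition with the checks.** Divide women by age (under 50, 50 to 59, 60 or over) and by menses in the last 12 months (yes, no), which gives 3 × 2 = 6 groups.

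| Age | Menses in last 12 months | Past child-bearing potential by the definition? | Self-report, urine test and monthly assessment stated? |
|---|---|---|---|
| Under 50 | Yes | No | Yes |
| Under 50 | No | No | Yes, where child-bearing potential exists |
| 50–59 | Yes | **No** | **No** |
| 50–59 | No | Yes | Not needed |
| 60 or over | Yes | Yes | Not needed |
| 60 or over | No | Yes | Not needed |

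The definition clears three groups and the checks reach two. The remaining one, 50 to 59 with menses in the last 12 months, has neither. Per woman, the stated checks there are 0 urine tests and 0 monthly assessments. A woman under 50 with child-bearing potential has 1 urine test and about 3 monthly assessments, taking monthly to mean Months 1, 2 and 3.

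**2. Ask whether such a woman can enroll.** The inclusion and exclusion criteria set no upper age limit, and nothing in them removes this group. She can.

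**3. Look for a check elsewhere.**

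- Baseline and Month 3 visits (Section 5): questionnaires and clinical data, with blood drawn for vitamin C and isoprostane. No pregnancy test.
- Phone calls (Sections 5 and 8): pill-taking, adverse events, symptom burden and quality of life. No pregnancy question.
- Baseline safety assessment (Section 8): supplements, creatinine and kidney stones.
- Adverse event checklist (Section 10): diarrhea, nausea, bloating and an open item for other events. No pregnancy item.

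None of these closes the gap.

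**Size.** The documents do not give the age or sex mix, so the share of the 42 participants in this group has to be assumed:

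- 0% × 42 = 0 women
- 1% × 42 = 0.42 women
- 5% × 42 = 2.1 women

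These count women to whom the rule would apply. They do not estimate pregnancies.

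**The case against.** The best defence is that this is a slip of drafting rather than an unsafe rule. Staff already ask women of 50 to 59 about their menses, and the question has a point only if the answer matters, so the intent to treat a menstruating woman as potentially fertile is visible. Exclusion (f) covers her, and both the research assistant's screening and the treating provider's approval stand between her and enrollment. Pregnancy at this age is rare, the documents report no hazard from oral vitamin C in pregnancy, and one third of participants (14 of 42) receive placebo. The consent form is also not part of the text reviewed and could carry a pregnancy instruction.

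Much of this stands as a limit on the weight of the point. It does not remove the gap. The exclusion and the provider's approval catch a pregnancy that someone knows about. For women under 50 the protocol adds a urine test to self-report, so it does not itself regard the bare exclusion as enough where child-bearing potential remains. Rarity does not explain the cut-off either: the protocol chose not to clear every woman at 50, and the point only holds it to that choice. As for intent, a research assistant working from an explicit age limit would have no instruction to test her.

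**Conclusion.** The point holds. The age limit on the pregnancy checks contradicts the protocol's own definition and leaves one eligible group, women of 50 to 59 with menses in the last 12 months, without a stated test or monthly assessment. It is a minor safety-rule error, with no bearing on the primary endpoint, the power statement or the analysis.

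The gap itself rests only on the wording of Section 3 and on the absence of a pregnancy procedure in the rest of the protocol text. The head-count of 0 to 2.1 women rests on assumed shares of 0% to 5% and shows scale only; the true number could be zero. No probability of pregnancy or of harm can be derived from the documents.

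**What to change.** In Section 3, replace the opening phrase that limits the checks to women under 50 with wording tied to the definition, for example: *For all women who are not past child-bearing potential (women under 50 with child-bearing potential, and women aged 50 to 59 who have menstruated within the past 12 months)*. The rest of the sentence stays as it is. With this change, none of the six groups is left without either clearance or a check.

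The cost is one phrase in the protocol, plus one urine test and a monthly question for each woman affected, which is 0 to about 2 women under the shares assumed above. Menstrual history is already asked at ages 50 to 59. The monthly question can be added to the Month 1 and Month 2 calls and to the Month 3 visit, all of which are already scheduled.
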